2.3.1. Risk Assessment

Potential Risk of Clinical Significance	Summary of Data/Rationale for Risk	Mitigation Strategy
Study Intervention: IW-3300		
Potential for diarrhea and secondary dehydration	These are class effects of GC-C agonism or effects observed in nonclinical safety pharmacology and toxicology studies of IW-3300.	Intrarectal administration will likely decrease the risk of diarrhea and subsequent dehydration. The study design includes dose escalation to closely monitor subject safety and tolerability at each dose level before dosing with a higher dose; a Dose Escalation Committee will conduct blinded reviews of all the safety parameters of the dosing cohort through Discharge (Day 8) in order to make decisions regarding escalation to the next dose. Orthostatic vital sign measurements will be taken to evaluate the potential for volume depletion. The daily bowel movement (BM) frequency and stool consistency will be monitored in real time to evaluate changes in bowel habits and the potential risk of diarrhea. Stopping rules will also be in place to evaluate continued dosing (Section 7.1.1); dosing within a cohort may be temporarily suspended in the event of a diarrhea or dehydration serious adverse event (SAE); ≥ 1 subject with Grade 3 diarrhea (increase from baseline of >7 stools per day and/or watery stools [Bristol Stool Form Scale {BSFS} score of 7] resulting in a limiting of self-care activities) or dehydration (hospitalization indicated); or ≥ 3 subjects with Grade 2 diarrhea (increase from baseline of 4 to 6 stools per day and/or watery stools [BSFS score of 7] resulting in a limiting of instrumental activities) or dehydration (intravenous fluids indicated).

Potential Risk of Clinical Significance	Summary of Data/Rationale for Risk	Mitigation Strategy

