5.1. Inclusion Criteria

Subjects are eligible to be included in the study only if all of the following criteria apply:

Age

1. Subject is 18 to 60 years of age, inclusive, at the time of signing the ICF.

Type of Subject and Disease Characteristics

2. Subject is medically healthy with no clinically significant findings during medical evaluation including physical examination, 12-lead ECG, and clinical laboratory tests (serum chemistry, hematology, urinalysis, and urine drug and alcohol screen). (NOTE: In making this determination, the investigator or designee will consider whether any finding could prevent the subject from performing any of the protocol-specified assessments, could represent a condition that would exclude the subject from the study, could represent a safety concern if the subject participates in the study, or could confound the study-specified assessments [eg, incontinence, overactive bladder, prostatitis, urinary tract infection]).
3. Subject has normal formed bowel movements (≥ 3 per week and ≤ 3 per day; average BSFS score of >2 and <6 , as reported in the BBMD during the 7 days before Check-in [Day -1]).
4. Subject agrees to refrain from making any new or major lifestyle changes (eg, new diet or exercise regimen) from the Screening Visit until after the Follow-up Phone Call on Day 21.
5. If subject is ≥ 45 years of age, subject is compliant with colorectal cancer screening guidelines according to the American College of Gastroenterology (ACG) Clinical Guidelines: Colorectal Cancer Screening 2021. (8)

Weight

6. Subject's body mass index (BMI) is within the range 18.5 to 35.0 kg/m² (inclusive) at the Screening Visit.

Sex

7. Male and female subjects
 - a. Female subject is of nonchildbearing potential (ie, women who are postmenopausal [greater than 12 months without menses] or who have had a procedure such as a bilateral oophorectomy, bilateral salpingectomy, or hysterectomy).
 - b. Subject is willing to abstain from sexual intercourse during the period of confinement in the CRU.

- c. Male subject and female partner(s) are willing to use a double-barrier method of contraception during the study (eg, diaphragm with spermicide plus a condom, condom with spermicide plus a diaphragm or cervical cap), from the Screening Visit until after the Follow-up Phone Call on Day 21.

Informed Consent

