7.5. Bladder and Bowel Movement Diary (BBMD)

The analysis of the bladder and bowel movement diary (BBMD) parameters will be based on the Safety Analysis Set. Subjects will enter BM-related information into a paper diary, the BBMD, on an event-driven basis (ie, following each BM) during the Screening Period (beginning at Day -8) and throughout the Clinic Period. The BM related information will include the day and time of BMs and a report of stool consistency for each BM using the Bristol Stool Form Scale (BSFS) (1=Separate hard lumps like nuts [difficult to pass], 2=sausage shaped but lumpy, 3=like a sausage but with cracks on surface, 4=like a sausage or snake, smooth and soft, 5=soft blobs with clear-cut edges (passed easily), 6=fluffy pieces with ragged edges, a mushy stool and 7=Watery, no solid pieces [entirely liquid]).

Subjects will complete the bladder portion of the BBMD in the morning of Dosing Day 1 (which represents the baseline responses) and each subsequent morning from Dosing Day 2 thru Discharge Day 8. The bladder diary will include the following questions:

In the past 24 hours...

- Did you have to urinate more frequently than normal? (yes/no)
- How many times did you urinate? (0 to 2; 3 to 6; 7 to 10; or more than 10)
- Did you feel the strong need to urinate with little or no warning? (yes/no)
- Did you have to get up to urinate during the night more frequently than usual? (yes/no)
- How many times did you have to get up at night to urinate? (0, 1, 2, 3+ times)
- Did you have pain or burning in your bladder or pelvic area? (yes/no)

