7.5.1. BBMD Analysis

BM data will be summarized by treatment for the baseline period and for the post-baseline period covered by the $7 \times 24 = 168$ hours after the first dose of study drug using descriptive statistics. Change from baseline for the following BM parameters will be calculated:

- BM frequency
- Stool consistency (BSFS)

The baseline period for BM data is exactly 1 week and consists of the seven 24-hour periods that end at the time of first dose. Baseline values will be derived from the BBMD data collected during that period. The baseline BM daily frequency rate (BMs per day) will be calculated as the number of BMs the subject reports during this period divided by 7. Baseline stool consistency will be calculated as the average of the non-missing BSFS scores associated with the BMs reported by the subject during this period.

For BM data, the postdosing frequency and averages will be based on events and reports that occur during the seven 24-hour periods that start on Day 1 at the time of dosing and end on Day 8. Change from baseline will be defined as the postdosing values minus the baseline value. The data will be provided in listings as well.

The data regarding bladder symptoms and urination is categorical. The baseline values are simply the responses to the 6 relevant questions asked, predose, in the morning of Dosing Day 1, and the postdosing values are the responses to the BBMD on Days 2 through 8.

For the bladder symptoms and urination data, shift tables by study day will be created for each of the 6 questions, showing the responses for the 24 hours before dosing (completed on the morning of dosing, Day 1) versus the responses for the seven postdose 24-hour periods.

For the Day 1 pre-dosing Bladder and Urination data, summary analyses will only include diaries that were completed before dosing. Any diaries that were completed after the first dose will not be used. Similarly, for the Day 2 Bladder and Urination diary, only diaries that were completed between 20 and 32 hours after dosing will be used, to avoid overlap with pre-dosing and with Day 3. A similar 12 hour window will be used for the BBMD diaries for days 3 through 8.

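### Stool form is summarised only as a mean Bristol score, so watery stools are listed but never tabulated by treatment group

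*SAP*

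**What the plan says.** SAP 7.5 has subjects score every bowel movement (BM) from 1 (hard lumps) to "7=Watery, no solid pieces [entirely liquid". SAP 7.5.1 then reduces the scores to one number per subject per period. For baseline: "Baseline stool consistency will be calculated as the average of the non-missing BSFS scores associated with the BMs" reported in the seven 24-hour periods ending at first dose. After dosing, "the postdosing frequency and averages will be based on events and reports that occur during the seven 24-hour periods" starting at the Day 1 dose, which is a single pooled window of 168 "hours after the first dose of study drug using descriptive statistics". Change from baseline is the difference between the two averages. The only other planned output for bowel data is a listing: "The data will be provided in listings as well".

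Protocol 2.3.1 puts diarrhea first among the potential risks, calls it a class effect, and names diary monitoring as a mitigation: "stool consistency will be monitored in real time to evaluate changes in bowel habits and the potential risk of diarrhea". Its Grade 3 diarrhea description includes "increase from baseline of >7 stools per day and/or watery stools [Bristol Stool Form Scale {BSFS} score of 7", tied to limitation of self-care. The Grade 2 description is built the same way, with a smaller rise in frequency and limitation of instrumental activities.

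Protocol 9.4.5 asks for descriptive statistics on stool consistency at each assessment timepoint. It does not ask for a BSFS 7 count, and SAP 7.5.1 does not carry the by-timepoint summary over for bowel data.

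**The concern.** BSFS is an ordinal scale, and for a drug of this class the harm of interest lies at its upper end. A mean over all of a subject's stools lets hard stools cancel watery ones and lets formed stools dilute them. Averaging again over six subjects dilutes further. The minimum and maximum planned in SAP 11.1.1 would be those of subject averages, so they cannot reveal a single watery stool.

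The SAP does not rely on means alone for its other safety measures. Laboratory values (7.2), vital signs (7.3) and ECGs (7.4) each get a count of subjects with extreme values. Orthostatic hypotension gets a subject count, and the six bladder items get shift tables by study day. Stool form gets neither a count nor a shift table.

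At stake is whether the diary, the systematic stool-by-stool record, can show how many subjects on each dose and on placebo passed watery stools.

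**Working it through.** The plan states no figure for this analysis, and no sample size calculation was done, so there is nothing to reproduce. The check is arithmetic on the planned summary.

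**Inputs from the documents.** BSFS runs from 1 to 7, with 7 watery (SAP 7.5). The summary is a per-subject mean over 7 × 24 = 168 hours (SAP 7.5.1). Each cohort has 6 active and 3 placebo subjects (SAP 4.1.1), so two cohorts give 6 pooled placebo subjects.

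**Assumed inputs.** The stool mixes, a usual stool of type 4, and the SD used in step 5.

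1. *Offsetting.* Three stools at 2, five at 4 and two at 7: (3×2 + 5×4 + 2×7)/10 = 40/10 = 4.0. This equals the mean of ten type 4 stools.

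2. *Dilution within a subject.* If a fraction f is watery and the rest are type 4, the mean is 7f + 4(1 − f) = 4 + 3f. One in ten gives 4.3, a shift of 0.3. Six in ten gives 5.8, a shift of 1.8.

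3. *Dilution by pooling days.* Take one type 4 stool on each of six days and nine watery stools on the seventh. The weekly mean is (6×4 + 9×7)/15 = 87/15 = 5.80, while the mean for that day alone is 7.0. The weekly frequency is 15/7 = 2.14 per day against an assumed baseline of 1.

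4. *Dilution across a group.* One subject with five of eight stools watery has a mean of (5×7 + 3×4)/8 = 5.875. With the other five subjects at 4.0, the group mean is (5×4 + 5.875)/6 = 4.31.

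5. *Illustration of a group comparison.* Suppose 4 of 6 active subjects each have one watery stool in ten and no placebo subject does. The expected difference in means is (4/6) × 0.3 = 0.20. The standard error is SD × √(1/6 + 1/6) = 0.577 × SD, and by the normal approximation P(difference ≤ 0) = Φ(−0.20/SE).

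| Assumed SD of change | SE | P(difference ≤ 0) |
|---|---|---|
| 0.4 | 0.23 | 0.19 |
| 0.6 | 0.35 | 0.28 |
| 0.8 | 0.46 | 0.33 |

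The count for the same data would read 4/6 against 0/6. Both the SD range and the 4-to-0 contrast are assumptions, and the documents give no basis for either.

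6. *Precision of a count.* One of six subjects is 16.7%, with an exact 95% interval of 0.4% to 64.1%. Any such count is descriptive only.

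**The case against.** The strongest reply is that the diarrhea signal is not lost. TEAE incidence is the primary endpoint and is tabulated by preferred term, CTCAE grade and relationship (SAP 7.1). BM frequency is summarised separately, and with at most 27 subjects a reader can go through the stool listing line by line. Dose escalation rests on blinded review of all safety and tolerability data (Protocol 6.3.2 and 6.6), not on this table. All of that stands. It does not supply a comparison of watery stools by treatment: a listing makes none, frequency says nothing about form, and the TEAE tables depend on what is reported as an adverse event, for which Protocol 8.3.2 prefers open-ended questioning.

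Three stronger readings are tempting, and the documents do not support them.

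- *The protocol defines diarrhea by BSFS 7.* It does not. Watery stool is joined by and/or to a rise in frequency and tied to limitation of activities, so a count of subjects with a BSFS 7 stool would not reproduce the grades.
- *A mostly watery week would pass as normal because its mean lies within* "average BSFS score of >2 and <6". That range is an eligibility criterion (Protocol 5.1), and the SAP never applies it to postdose values. It reports change from baseline, and a change of +1.8 from a baseline of 4 would be plain to see.
- *Daily summaries would not help.* They would help in part. In step 3 the affected day stands out at 7.0. An isolated watery stool among formed stools on the same day would still be diluted.

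The step 5 probabilities also correspond to no planned decision, since Protocol 9.1 plans no hypothesis testing. Even 4/6 against 0/6 gives a two-sided Fisher p of about 0.06 (2 × 15/495).

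**Conclusion.** The point holds as a gap in the planned tables. SAP 7.5.1 gives no diary-based count of watery stools by treatment, although watery stool is part of the protocol's own diarrhea descriptions and other safety measures get counts of extreme values. The loss is greatest for isolated or scattered watery stools (a shift of 0.3 for one in ten) and for mixed patterns (a shift of zero in step 1). It is smallest for a heavily affected subject, whose change from baseline would be clear.

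It would be wrong to infer that diarrhea would go undetected or that the SAP breaks a protocol commitment to count BSFS 7 stools; there is no such commitment. The offsetting and dilution results are exact for the stool mixes shown. The group probabilities illustrate only an assumed SD of 0.4 to 0.8 and a chosen contrast. This is a worthwhile, inexpensive improvement to a supportive safety summary.

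**What to change.** Keep the mean BSFS and its change. Add to SAP 7.5.1, by treatment group with pooled placebo as the named comparator:

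- number and percentage of subjects with at least one BSFS 7 stool;
- the same for BSFS 6 or 7;
- number of such stools per subject.

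Present each for the baseline period, for the whole postdose period, and for each 24-hour postdose period. The last also brings the bowel data into line with the by-timepoint summary in Protocol 9.4.5. State that the counts are descriptive and are not a substitute for CTCAE grading.

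The cost is a paragraph of SAP wording and a few table rows from data already collected. Study conduct does not change. One caution should be written in: some BSFS 7 entries may be expelled enema fluid. Placebo subjects receive the same 20 mL enema, so the counts must be read against placebo and not on their own.

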^f For orthostatic blood pressure and pulse measurements, the subject must lie quietly for ≥ 5 minutes before supine/semisupine blood pressure and pulse measurements are taken, then assume standing position for 3 minutes before standing blood pressure and pulse measurements are taken. If a subject has orthostatic symptoms upon standing (eg, palpitation, dizziness), they will be assisted and asked to lie down without waiting the 3 minutes for vital sign assessment. Orthostatic measurements may be taken at other vital signs collection timepoints if clinically indicated, at the discretion of the investigator. When applicable, vital sign measurements will be obtained before blood draws.

^g ECGs should be obtained after the subject has been supine for at least 5 minutes. At each timepoint required, 3 individual ECG tracings should be obtained as closely as possible in succession, but no more than 2 minutes apart. The full set of triplicates should be completed in less than 4 minutes.

^h Elevated inflammatory markers (ESR, CRP), and/or relevant symptoms (eg, rectal pain, hematochezia) may be suggestive of colonic inflammation; subjects with these signs or symptoms should undergo recto-sigmoidoscopy. If this is negative, a colonoscopy may be performed after a discussion between the investigator and the Sponsor.

ⁱ HCG at Screening will be a blood-based test. HCG at Check-in/Day -1 will be a urine-based test.

^j The BM portion of the BBMD will be completed by the subject on an event-driven basis. For subjects with Screening Visits earlier than Day -9, CRU staff will call subjects on Day -9 to remind them to begin recording their BMs in the BBMD the following day, answer any questions, and provide additional BM pages via email, if needed. Bladder information in the BBMD will be collected predose on each dosing day, with a 24-hour recall period at each timepoint.

^k CRU staff will review the subject's Screening Period BBMD at Check-in to confirm that subjects have at least 3 bowel movements during the 7 days prior to Check-in (Days -8 through -2) and no more than 3 bowel movements per day to be eligible for the study; CRU staff will collect the subject's Clinic Period BBMD at Discharge.

^l Subjects will remain at the CRU from Check-in (Day -1) through Discharge (Day 8).

^m Subjects will fast for at least 6 hours prior to dosing on Days 1 through 7 and for at least 1 hour following dosing. During these times, water is permitted.

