ⁿ Study drug (IW-3300 or placebo low-volume enema) will be administered rectally once daily, after a fast of at least 6 hours; water is permitted. Subjects will be encouraged to empty their bowels in the morning prior to dosing, if possible. Subjects will be instructed to lie on their left side with their left leg extended and their right leg slightly bent. Study drug will be dispensed in capped syringes with a separately packaged colon tip applicator. The CRU dosing staff will remove the cap from the syringe, attach the colon tip applicator, prime the syringe and applicator to 20 mL, and slowly administer by inserting the contents of the syringe into the rectum. After the full dose has been administered, subjects will lie on their left side for at least 30 minutes to allow the liquid to distribute throughout their intestines, followed by at least 30 additional minutes in the semisupine position. CRU staff will monitor subjects for leakage of the study drug from the rectum during the initial 30 minutes post administration. Subjects should avoid using the bathroom and hold in the enema for as long as possible (at least 1 hour).

^o PK blood draws at 0.5- and 1-hour postdose should be collected while the subject maintains the position noted in the dosing instructions above.

^p At Check-in/Day -1, the subject will bring in a stool sample using the sample collection kit issued by the site. Between Day 7 (postdose) and Day 8 (predischarge), the first stool passed will be collected. If no stool is passed during this time, the subject will be discharged with a stool collection kit and asked to return the sample to the CRU.

^q The predose hemoccult testing may be performed using a stool sample obtained any time from Check-in (Day -1) to predose. If the subject does not produce a stool sample, stool that is present on the Day 1 (predose) digital rectal examination may be used. The Discharge (Day 8) hemoccult testing may be performed using a stool sample obtained any time from postdose on Day 7 to Discharge (Day 8). If the subject does not produce a stool sample, stool that is present on the Discharge (Day 8) digital rectal examination may be used.

^r CRU staff will contact subjects by phone for safety follow-up (at the discretion of the investigator, subjects may be requested to return to the CRU for their follow-up contact).

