Protocol C3300-102**CLINIC PERIOD****Subject Number: 001 - _____**Study Visit: _____
Day -1 through Day 8 Date: _____, _____, _____
Month Day Year**BLADDER AND BOWEL MOVEMENT DIARY**

Bladder and Urination	
Time of Completion: _____ : _____  AM  PM	
Please answer the questions below upon awakening for the day, thinking back over the past 24 hours	
In the past 24 hours...	
1	Did you have to urinate more frequently than normal?  Yes  No
2	How many times did you urinate?  0-2  3-6  7-10  more than 10
3	Did you feel the strong need to urinate with little or no warning?  Yes  No
4	Did you have to get up to urinate during the night more frequently than usual?  Yes  No
5	How many times did you have to get up at night to urinate?  0  1  2  3 or more
6	Did you have pain or burning in your bladder or pelvic area?  Yes  No

Bowel Movements		
Did you have a Bowel Movement today?  Yes  No		
If yes, please complete the table below.		
Please complete one row below for each bowel movement (BM) . If you have more than one BM in a day, please complete additional rows as needed. At the end of each day, please confirm that all BMs for that day have been entered and complete a row for each BM you may have forgotten to record.		
Time of Bowel Movement	Describe the bowel movement form (Please refer to the Bristol Stool Form Scale)	Initials
_____ : _____  AM  PM	Type:  1  2  3  4  5  6  7	
_____ : _____  AM  PM	Type:  1  2  3  4  5  6  7	

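### The 20-to-32-hour window for bladder diaries does not avoid overlap as the SAP says, and on dosing days it admits diaries completed after that day's dose

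*SAP*

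**What the plan says.** The bladder part of the diary has six questions with a 24-hour look-back. Three places set when it is completed:

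- Protocol 1.3 (Schedule of Activities, footnote j; repeated in SAP 11.3): "Bladder information in the BBMD will be collected predose on each dosing day, with a 24-hour recall period at each timepoint". Protocol 4.1.1.2 (Clinic Period) says the same.
- SAP 7.5: completed on the morning of Day 1 as baseline, then "each subsequent morning from Dosing Day 2 thru Discharge Day 8".
- The Clinic Period form in SAP 11.4: "Please answer the questions below upon awakening for the day, thinking back over the past 24 hours".

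SAP 7.5.1 then decides which diaries enter the summaries. For Day 1: "Any diaries that were completed after the first dose will not be used". For Day 2: "only diaries that were completed between 20 and 32 hours after dosing will be used, to avoid overlap with pre-dosing and with Day 3". For the rest: "A similar 12 hour window will be used for the BBMD diaries for days 3 through 8". The output is a shift table by study day for each question, setting the baseline response "versus the responses for the seven postdose 24-hour periods".

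**The concern.** The rule limits the time of completion, but what is tabulated is the period recalled. A 24-hour recall combined with a 12-hour completion window lets the recalled period slide by up to 12 hours. Part of a Day 2 response can then describe time before any drug, or time after the second dose, although the SAP gives the window as the means of preventing this.

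The rule also treats the days differently. A Day 1 diary completed after that day's dose is dropped, while a Day 2 to Day 7 diary completed hours after that day's dose is accepted and counted towards the previous dose. With 6 active subjects per dose level, one misattributed or excluded response is visible in a shift table. These questions are in the study to pick up unwanted effects on the bladder.

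**Working it through.** **Inputs.** Window 20 to 32 h after dosing (SAP 7.5.1). Recall 24 h (Protocol 1.3; form in SAP 11.4). Study drug "will be administered rectally once daily, after a fast of at least 6 hours" (SAP 11.3). Assumption: a dosing interval I of 24 h, with 22 to 26 h checked, because no clock time of dosing is given. Second assumption: the windows for Days 3 to 8 run from the previous day's dose, because the SAP names no anchor for them.

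**The plan's own figure.** 32 − 20 = 12 h, which agrees with the width the SAP states.

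**1. What a Day 2 diary recalls.** A diary completed t hours after the first dose covers t − 24 to t. Hours before the first dose = max(0, 24 − t). Hours after the second dose = max(0, t − I), here with I = 24.

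| t (h) | Period recalled (h) | Before first dose (h) | After second dose (h) |
|---|---|---|---|
| 20 | −4 to 20 | 4 | 0 |
| 22 | −2 to 22 | 2 | 0 |
| 24 | 0 to 24 | 0 | 0 |
| 28 | 4 to 28 | 0 | 4 |
| 32 | 8 to 32 | 0 | 8 |

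With 24-hour dosing only t = 24 is free of both, so no window of positive width can meet the stated aim. A Day 2 diary completed before the second dose (t < 24) always recalls some time before the first.

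**2. Overlap with Day 3.** Under the assumed anchor the Day 3 window is 20 + 24 = 44 h to 32 + 24 = 56 h. The completion windows are separate (44 − 32 = 12 h apart). The recalled periods need not be: a diary at 32 h covers 8 to 32 h and one at 44 h covers 20 to 44 h, which share 32 − 20 = 12 h.

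**3. Acceptance after the next dose, Days 2 to 7.** (32 − 24) / 12 = 8/12 = 67% of the window lies after that day's dose. For I = 22 h it is 32 − 22 = 10 h; for I = 26 h it is 32 − 26 = 6 h. Day 8 has no dose, so this does not arise there.

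**4. The lower limit and diaries completed on awakening.** A diary completed g hours before the next dosing time has t = I − g, and is rejected when I − g < 20, that is, when g > I − 20 = 4 h (2 h for I = 22, 6 h for I = 26). As illustrations only: with dosing at 08:00 a subject would have to wake before 04:00 to be rejected; at 10:00, before 06:00; at 12:00, before 08:00.

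**5. What the lower limit protects.** On Day 2 it caps recall of time before the first dose at 24 − 20 = 4 h; a diary at 18 h would recall 24 − 18 = 6 h. On later days it protects nothing of that kind. A Day 3 diary completed 18 h after the second dose is at 24 + 18 = 42 h and recalls 18 to 42 h, all of it on treatment.

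**The case against.** The best defence is that avoiding overlap refers to when diaries are completed. The sentence follows a Day 1 rule about completion time, and under the natural anchor the completion windows are separate, so no diary counts for two days. That much stands. It does not rescue the stated purpose, because the shift tables are said to show 24-hour periods before and after dosing.

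A second defence is that late diaries should be rare: subjects are confined to the unit, the protocol asks for completion before the dose, and the form says on awakening. So 8 h is the edge of what is allowed, not an expected value. This is fair, but it is also a reason for the SAP not to accept such diaries.

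The documents do not support four stronger readings that a reader might infer:

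- *The window rejects compliant diaries, perhaps all seven for a subject.* This needs waking more than about 4 h before dosing. No clock times are given, and the instruction to try to empty the bowels that morning before dosing points to morning dosing. Early dosing would leave instructed diaries accepted.
- *The windows for Days 3 to 8 are fixed at 44 to 56 h and so on.* That is an assumption; the missing anchor is itself a gap.
- *The shift tables are the only view of bladder effects.* Protocol 9.4.5 also plans descriptive statistics for urinary frequency, urgency, nocturia and bladder or pelvic pain, and symptoms reported as adverse events enter the TEAE tables.
- *The 20-hour limit should go on every day.* On Day 2 it is the only cap on recall of time before the first dose.

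**Conclusion.** The point holds in a limited form. With a 24-hour recall and a nominal 24-hour dosing interval, the Day 2 window does not avoid overlap: up to 4 of the 24 recalled hours can precede the first dose, or up to 8 can follow the second. On Days 2 to 7, about 8 of the 12 accepted hours (6 to 10 h for intervals of 26 to 22 h) come after that day's dose. That conflicts with the protocol's collection rule and with the SAP's own treatment of Day 1. For Days 3 to 7 it assumes that each window runs from the previous day's dose.

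Rejection of a diary completed on awakening is possible but conditional, and its frequency cannot be estimated from the documents. The consequence is confined to descriptive safety shift tables; the primary endpoint is unaffected. The correction is worth making before database lock because it costs little and follows the protocol's own rule.

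**What to change.** In SAP 7.5.1:

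- **Days 2 to 7:** use the nominal-day diary only if it was completed before that day's dose.
- **Day 8:** use the diary completed that morning before discharge.
- **Anchor:** state that hours are counted from the previous day's dose on every day.
- **Lower limit:** drop the 20-hour limit for Days 3 to 8. For Day 2, keep it, or keep shorter diaries and flag them.
- **Wording and listing:** delete the statement that the window avoids overlap, and list hours since the previous dose for every diary, including those left out of the summaries.

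The cost is a few lines of text and programming. There are two drawbacks. A diary completed shortly after the next dose leaves the summaries, although its recall may nearly match the intended 24 hours; it should remain in the listing. Up to 4 h of recall before the first dose also stays in Day 2, and more if diaries under 20 h are flagged and kept.
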